### Study Protocol

The focus of the project is to assess the impact of slow-wave disruption on plasticity in major depression. Following enrollment, subjects will establish a regularized bed/wake schedule based on their usual bed/wake time monitored in-home by sleep diary and actigraphy for 5 days. All subjects will then spend two nights in the sleep lab – a baseline night and an experimental slow-wave disruption night. On the experimental night, an acoustic tone will be used to decrease slow wave activity (SWA) without waking the subject. The order of nights will be determined via randomization. Between all visits, participants sleep at home on a regular sleep schedule, confirmed by sleep diaries, and actigraphic recordings.

All participants take part in 3 visits to the laboratory:

1. Visit 1: A screening and consenting visit involving informed consent, clinical assessment interviews, self-report measures, and an orientation to TMS and slow-wave disruption procedures.
2. Visit 2: A baseline night in the laboratory where participants spend the night in our sleep laboratory having their sleep monitored, followed by a morning blood draw, and assessment of mood via the clinician-administered Hamilton rating scale for depression, and battery of questionnaires including the Beck Depression Inventory II, two Visual Analogue Scales measuring positive and negative mood, respectively, and Karolinska Sleepiness Scale to assess sleepiness tasks. Additionally, participants will complete a battery of tasks including a resting EEG protocol to assess waking EEG theta power, and two learning and memory tasks, the N-Back, and Paired Associated Learning, followed by the TMS protocol, where motor evoked potentials and intracortical facilitation will be assessed.
3. Visit 3: A slow-wave disruption night where slow-wave activity will be experimentally reduced using acoustic tones administered when sleep technologists detect slow-waves from real-time EEG monitoring, followed by the same procedures as detailed in Visit 2.

Note that the order of baseline night and slow-wave disruption night is counterbalanced, with all participants undergoing both nights.

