### Statistical Analysis Plan

SPECIFIC AIM 1: Compare multiple, indirect indices of synaptic strength and plasticity in patients with MDD to healthy controls, and to their relationship with SWA. Aim 1 will be achieved by testing null hypotheses that the mean values at baseline are equal between HC and MDD. Hypotheses will be tested using two-sample t-tests with adjustment for multiple outcomes addressed using the methods described above. Regression and correlation analyses will be used to evaluate the degree to which synaptic strength/plasticity variables are associated with SWA. Predictions: (Hypothesis 1.1) The MDD group will demonstrate lower values of synaptic strength (lower total theta power, lower amplitude TMS-evoked potentials) and plasticity (lower levels of serum-derived BDNF, worse performance on behavioral measures of learning and memory) compared to HC at baseline. (Hypothesis 1.2) In those with MDD there will be a positive relationship between measures of synaptic strength and plasticity (total theta power, TMS-evoked potentials, BDNF, performance on behavioral measures) and SWA in the first

NREM period that is not present in HC, such that lower values of synaptic strength and plasticity are predicted for subjects with lower SWA.

SPECIFIC AIM 2: Determine if SWA disruption alters measures of mood, and measures of synaptic strength and plasticity in a sample of individuals with MDD. Regression will be used to model if SWA is directly associated with mood, and synaptic strength/plasticity variables.

Predictions: (Hypothesis 2.1) There will be a positive relationship between SWA and negative mood scores (HAM-D, Negative VAS), such that lower SWA will be associated with lower negative mood scores. (Hypothesis 2.2) There will be a positive correlation between reductions in SWA and improvements in synaptic strength/plasticity variables (total theta power, TMS-evoked potentials, BDNF, performance on behavioral measures), such that subjects with the greatest reductions in SWA will be expected to have the largest improvements in synaptic strength/plasticity endpoints. Since the scientific hypothesis is clearly one-sided, one-sided tests of the hypotheses of zero correlation will be performed controlling the type 1 error rate for the set of 5 comparisons using Holm-Bonferroni method described above. Therefore, the first test will be conducted at a 1-sided type 1 error rate of  $\alpha=0.01$ .

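### Aim 2 asks whether slow-wave disruption alters mood and plasticity, but the supplied SAP names no test or estimate of the mean disruption-minus-baseline change

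*Combined protocol and SAP*

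**What the plan says.** The Study Protocol section describes a within-person design. All participants have both nights, "The order of nights will be determined via randomization", and the disruption night is "followed by the same procedures as detailed in Visit 2". The outcomes are therefore measured the same way after each night.

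The SAP states Aim 2 as: "Determine if SWA disruption alters measures of mood, and measures of synaptic strength and plasticity in a sample of individuals with MDD". Three analysis statements follow.

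- General method: "Regression will be used to model if SWA is directly associated with mood, and synaptic strength/plasticity variables".
- Hypothesis 2.1 (mood): "There will be a positive relationship between SWA and negative mood scores (HAM-D, Negative VAS"), with lower SWA going with lower negative mood.
- Hypothesis 2.2 (plasticity): "subjects with the greatest reductions in SWA will be expected to have the largest improvements in synaptic strength/plasticity endpoints". The tests are "one-sided tests of the hypotheses of zero correlation will be performed controlling the type 1 error rate for the set of 5 comparisons", by Holm-Bonferroni, the first at one-sided 0.01.

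For Aim 1 the SAP is explicit about the null, the night and the test: "Aim 1 will be achieved by testing null hypotheses that the mean values at baseline are equal between HC and MDD", by two-sample t-tests. Aim 3 repeats the Aim 1 and 2 analyses by sex. Its Hypothesis 3.2 compares plasticity difference scores between males and females with MDD, and its results are to be treated as hypothesis generating.

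**The concern.** The direct evidence on whether disruption alters an outcome is the randomised within-person contrast between the two nights. Aim 2 names no paired test, condition term or mean change for any outcome.

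The Hypothesis 2.2 test answers a different question: whether people with larger SWA reductions improve more. The order of nights is randomised, but the size of a person's SWA reduction is not, so this correlation is observational. It can miss an effect shared equally by everyone. It can also be significant when the average change is nil or adverse, and then be read as a benefit of disruption.

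For mood, and for the general regression, the text does not say whether baseline, disruption, both nights or change scores enter, or whether the association is within or between persons. Whether those models reflect the night contrast at all depends on a choice that is not written down and could be made after the data are seen.

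**Working it through.** **The plan's own figure.** Holm first step = overall alpha / number of tests = 0.05/5 = 0.01, which matches the stated value. The overall one-sided 0.05 is inferred from this.

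**Inputs.** From the documents: two nights per person, one-sided zero-correlation tests, first-step alpha 0.01. Assumed, because the documents give no N, SD or effect size: n = 40 (n = 20 in brackets), SD of improvement = 1, mean SWA reduction = 1, CV (SD/mean of SWA reduction) from 0.3 to 1.0, normal data, no period effect. Let x be a person's SWA reduction and y the improvement. Rejection rates are from simulation.

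**Step 1: the Hypothesis 2.2 test.** Since corr(x, y + c) = corr(x, y), a constant shift c for everyone has no effect on it. The paired test uses t = mean(y)/(SD/√n), with noncentrality 0.5 × √40 = 3.16 (0.5 × √20 = 2.24) for a 0.5 SD effect.

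| True state | Correlation, one-sided 0.01 | Paired, two-sided 0.01 |
|---|---|---|
| Uniform 0.5 SD benefit, r = 0 | 1% (1%) | 67% (30%) |
| Zero mean change, r = 0.5 | 85% (49%) | 1% (1%) |
| Mean worsening 0.5 SD, r = 0.5 | 85% (49%) | 67% (30%), as a worsening |

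**Step 2: the regression, read as a two-night within-person slope.** With a fixed effect per person and two nights, the slope is b = Σxy/Σx². Its approximate expectation, one-sided rejection rate at 0.01 and n = 40, for CV 0.3 to 1.0:

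| True state | Expected b | Rejects for benefit |
|---|---|---|
| Uniform 0.5 SD benefit | 0.5/(1 + CV²): 0.46 to 0.25 | 72% to 38% |
| Zero mean change, r = 0.5 | 0.5·CV/(1 + CV²): 0.14 to 0.25 | 7% to 48% |
| Mean worsening 0.5 SD, r = 0.5 | (−0.5 + 0.5·CV)/(1 + CV²): −0.32 to 0 | 0.4% or less |
| Improvement proportional to x (y = 0.5x + error) | 0.5 | 81% to 99% |

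The like-for-like comparator for the two 0.5 SD benefit rows is a one-sided paired test, at 77%. This slope is therefore sensitive to the night contrast, but it mixes mean change with dose-response.

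**Step 3: the choice of nights matters.** If only the disruption night enters, a uniform effect adds the same constant to every outcome and the slope does not move, so the rejection rate stays at 1% when there is no between-person relation. The sign can change too. In an illustrative model (n = 40, between-person slope −0.5, within-person slope +0.5), the fitted slope was −0.31 using the disruption night, −0.23 pooling both nights as independent, and +0.51 for change on change.

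**Step 4: does other text supply the contrast?** Hypothesis 3.2 uses difference scores, but compares them between the sexes, for plasticity only, in an exploratory aim. The SAP twice refers back to methods that are not in the supplied text. Both references concern multiplicity adjustment, not an Aim 2 contrast.

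**The case against.** The strongest reply is that Hypothesis 2.2 is the intended hypothesis and is tested correctly: the investigators predict dose-response, and a zero-correlation test matches that. This stands, and the correlations should stay. If improvement is proportional to SWA reduction, the two-night within-person slope even beats the one-sided paired test (81% to 99% against 77%). It would also rarely signal benefit if outcomes worsened on average. But the SAP does not say that this slope is the model, and power under one assumed shape does not supply an estimate of the mean effect.

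Difference scores are evidently planned variables, since Hypothesis 3.2 uses them, and describing them by sex would tend to show mean change. A change-score regression would also return the mean change as its fitted value at the mean SWA reduction. Neither is specified as an Aim 2 analysis.

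A reader might infer that nothing in the plan could detect an average effect of disruption. The documents do not support that, because the regression wording leaves the within-person reading open. Nor should all readings be weighed equally: a baseline-night-only regression contains no disruption data and is not a natural reading of this aim.

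The size depends on chosen scenarios. The 1% under a uniform effect is simply the alpha of the test, and a CV of 1.0 with normal data implies that about 16% of people gain SWA on the disruption night.

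**Conclusion.** The gap holds as a matter of specification. For Aim 2 the supplied SAP names no test or estimate of the mean disruption-minus-baseline change. Its one fully specified test is unaffected by a mean shift, and its regression does not state nights or level. At n = 40 and alpha 0.01, the consequence ranges from 1% against 67% for a uniform 0.5 SD benefit (correlation against two-sided paired test) to a modest loss or a gain if a two-night within-person slope is what is meant. These figures rest on assumed n, SD, CV and effect shape. The conclusion that the contrast is missing does not.

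This should be fixed before analysis. It does not invalidate the Hypothesis 2.2 tests, and the data for the contrast are already being collected. Confidence is medium, because some methods text to which the SAP refers is not in the supplied document.

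**What to change.** Add to Aim 2, for each named outcome (the 5 plasticity comparisons, HAM-D and Negative VAS), an order-adjusted within-person disruption-minus-baseline contrast with a confidence interval. This can be a paired difference adjusted for order, or a mixed model with condition, period, sequence and a random person intercept. Base the conclusion on whether disruption alters the outcome on this contrast. The same contrast then carries into the sex-stratified analyses of Aim 3.

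Keep the Hypothesis 2.2 correlations as the dose-response hypothesis, label them observational, and report them beside the mean contrast. State which nights enter the regression; if both do, separate a person's mean SWA from the within-person deviation.

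State the multiplicity role of both sets. Either the 7 contrasts form the confirmatory Holm family (first step 0.05/7 = 0.0071), with the correlations secondary or a separate declared family; or all 7 + 5 = 12 tests share one family (first step 0.05/12 = 0.0042).

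The cost is SAP wording and a few models, with no new data. First-step two-sided power for a 0.5 SD within-person effect (noncentral t, n − 2 df) goes from 67% at alpha 0.01 to 63% with 7 tests or 55% with 12 at n = 40, and from 29% to 25% or 19% at n = 20.

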SPECIFIC AIM 3: Explore if males with MDD are more sensitive to SWA and plasticity-related impairment. The MDD sample will be stratified by sex, resulting in two equal groups, males and females. The analyses described for Aims 1 and 2 will be repeated stratified by sex. Focus will be on descriptive comparisons of sex-specific effect sizes since the study is not powered for within sex comparisons. However, statistical comparisons between sex will be performed and where appropriate 95% confidence intervals for differences between sex in relevant effect sizes will be constructed in order to evaluate the likely ranges of sex-based differences. It is expected that sex differences, if any, are magnified in MDD and may be much smaller in HC. Therefore, if sex differences in HC appear relatively small, the analyses for Aim 3 will also compare male MDD and female MDD to all HC. Results from Aim 3 will be considered hypothesis generating. Predictions: (Hypothesis 3.1) MDD males will demonstrate lower SWA, and lower values of synaptic strength and plasticity (total theta power, TMS-evoked potentials, BDNF, performance on behavioral measures) compared to MDD females and HC at baseline. (Hypothesis 3.2) Males with MDD will also have larger synaptic strength and plasticity difference score values than females with MDD.

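### The Hypothesis 2.2 correlation of two within-subject changes has no term for night order; counterbalancing does not protect it from visit effects

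*Combined protocol and SAP*

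**What the plan says.** The Study Protocol section gives every participant both laboratory conditions: "All subjects will then spend two nights in the sleep lab", one baseline and one with acoustic disruption of slow waves. Order is randomised, and the section closes: "Note that the order of baseline night and slow-wave disruption night is counterbalanced, with all participants undergoing both nights". It describes no separate adaptation night in the laboratory. The morning battery, which includes the N-Back and a paired-associate learning task, is given after both nights; the disruption night is "followed by the same procedures as detailed in Visit 2". Whether alternate task forms are used is not stated.

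Under Specific Aim 2, the Statistical Analysis Plan says "Regression will be used to model if SWA is directly associated with mood, and synaptic strength/plasticity variables", and lists no covariates. Hypothesis 2.2 predicts that "subjects with the greatest reductions in SWA will be expected to have the largest improvements in synaptic strength/plasticity endpoints". For this, "one-sided tests of the hypotheses of zero correlation will be performed controlling the type 1 error rate for the set of 5 comparisons", by Holm-Bonferroni, with the first step at one-sided 0.01. No order, period, sequence or visit term is named. Aim 3 carries the same analysis forward: "The analyses described for Aims 1 and 2 will be repeated stratified by sex".

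The plan points back to methods that are not in the supplied text, but both references concern multiplicity. Order adjustment is therefore unstated rather than ruled out.

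**The concern.** A difference between the second and first visit, whatever its cause, adds to the disruption-versus-baseline change in one order and subtracts from it in the other. With balanced orders this averages out of the mean change, which is the usual reason for counterbalancing. Hypothesis 2.2 does not test a mean change. It tests whether two changes vary together across subjects. If both SWA and the outcome have a visit effect, order is a common cause of both changes and adds covariance that has nothing to do with slow-wave disruption.

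The plausible case is an unadapted first laboratory night, with lower SWA, together with practice on the two learning tasks. Both quantities are then higher at the second visit, the correlation is pulled down, and a true association on those tasks could be missed. If the two visit effects have opposite signs, the correlation is pushed up and the one-sided test rejects too often; the documents do not show which endpoint, if any, would behave that way. If only one of the two has a visit effect, no false correlation arises, but a true one is diluted. No visit effect is argued here for theta power, BDNF or the TMS measures.

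**Working it through.** **The plan's own figure.** Five comparisons with a first Holm step of 0.01 imply an overall one-sided level of 5 × 0.01 = 0.05. Equivalently 0.05/5 = 0.01, which reproduces. The overall level is implied, not stated. The documents give no sample size, SD, effect size or power, so nothing else can be reproduced.

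**Inputs.** From the documents: two nights, randomised and counterbalanced order (read as 1:1), correlation of two changes, one-sided 0.01. Assumed: 40 subjects with MDD (also 20 and 60), true within-order correlation r = 0.5, bivariate normal changes, and the visit effects below.

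**Model.** Let s = +1 if baseline is first and −1 if disruption is first. Let v_S and v_Y be the second-minus-first visit effects on SWA and on the outcome, in within-order SDs of the change score. Then

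- SWA reduction (baseline − disruption) = a − s·v_S
- improvement (disruption − baseline) = b + s·v_Y

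where a and b have correlation r. With 1:1 order the correlation actually tested is

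r* = (r − v_S·v_Y) / √[(1 + v_S²)(1 + v_Y²)].

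For r = 0.5 and both effects 0.3: (0.5 − 0.09)/1.09 = 0.38. For both 0.5: (0.5 − 0.25)/1.25 = 0.20. For r = 0 and both 0.5, the result is −0.20; with opposite signs it is +0.20.

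**Counterbalancing.** If a share q of subjects has baseline first, the induced covariance is proportional to 4q(1 − q), which is largest at q = 0.5. For effects of 0.5 SD with opposite signs, n = 40 and r = 0, the mean correlation is 0.20, 0.18 and 0.08 at q = 0.5, 0.7 and 0.9.

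**Rejection rates.** Simulated at one-sided 0.01 (at least 100,000 trials per setting), comparing the plain correlation (n − 2 df) with the partial correlation given order (n − 3 df).

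Power at r = 0.5, equal effects, both higher at the second visit:

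| Visit effect (SD) | r* | n = 20 | n = 40 | n = 60 |
|---|---|---|---|---|
| 0 | 0.50 | 49% | 85% | 97% |
| 0.1 | 0.49 | 45% | 82% | 96% |
| 0.2 | 0.44 | 36% | 72% | 90% |
| 0.3 | 0.38 | 23% | 53% | 75% |
| 0.5 | 0.20 | 4% | 11% | 18% |
| With order term, any effect | 0.50 | about 46% | about 84% | 96–97% |

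Other cases at n = 40:

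- Unequal effects, r = 0.5: outcome 0.3 and SWA 0.1 SD, 73%; outcome 0.3 and SWA 0.2 SD, 64%.
- Outcome effect only: power 81% (0.3 SD) and 73% (0.5 SD); type I error stays about 1%.
- Opposite-signed effects, r = 0: type I error 1.2%, 1.8%, 3.4% and 14% at 0.1, 0.2, 0.3 and 0.5 SD.
- With the order term, type I error is about 1% in every case.

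**The case against.** The mechanism is not in dispute; the case against is about reach and size.

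- **No visit effect is documented.** The first-night and practice effects are assumptions, and both must be present for the worse figures. This stands: the harm is conditional. At 0.1 SD the loss is about 3 points; the 11% figure needs the two orders to differ by a full SD (2 × 0.5) in mean change on both variables.
- **Reach and direction.** The argued case touches the learning tasks only, and there the bias is conservative. This also stands: the main risk is a missed association, and no endpoint has been identified for which error would be inflated.
- **A single true correlation.** At n = 40 and 0.3 SD on both, power goes from 33% to 12% at r = 0.3, and from 99.9% to 94% at r = 0.7. So the loss is 21, 32 and 6 points at r = 0.3, 0.5 and 0.7. It varies with r but does not vanish.
- **First-step alpha only.** Later Holm steps are less strict. At 0.05, the last step under the implied overall level, the 0.3 SD case at r = 0.5 goes from 96% to 78%, and the 0.3/0.1 SD case from 96% to 91%.
- **Tones may swamp the first-night effect.** If slow waves are suppressed in either position and a first-night effect acts mainly on the baseline night, the SWA shift halves. Power is then 69% rather than 53% (0.3/0.15 SD) and 38% rather than 11% (0.5/0.25 SD). This is a fair moderation of the size, and a substantial loss still remains.
- **The supplied plan may be incomplete.** An order term could sit in text not supplied. If so, the sponsor need only point to it.

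**Conclusion.** The concern holds. As supplied, the plan tests a correlation of two changes without the randomised night order, and counterbalancing does not protect that test. The harm depends on visit effects that the documents do not give: negligible at about 0.1 SD, a loss of about 32 points of power (85% to 53%) at 0.3 SD on both changes, and near-total at 0.5 SD, for n = 40, r = 0.5 and one-sided 0.01. The likely direction is lost power on the learning tasks rather than false positives. It should be fixed because Hypothesis 2.2 is the analysis for which the plan spells out error control over five comparisons, and adjusting for order removes the dependence on unknown visit effects at almost no cost. Confidence in the practical size is medium; the mechanism itself is exact under the additive model shown.

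**What to change.** For Hypothesis 2.2, pre-specify a regression of each outcome difference on the SWA difference plus night order (equivalently, a partial correlation given order). Test the SWA coefficient one-sided within the planned Holm-Bonferroni procedure. Use the same term when the analysis is repeated by sex in the exploratory Aim 3. Reporting the unadjusted estimate alongside would show how much order matters.

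The cost is a sentence in the SAP and one covariate already fixed by randomisation, using one degree of freedom. If there are no visit effects, power at r = 0.5 changes from 49.0% to 46.1% at n = 20, from 85.3% to 84.2% at n = 40, and from 96.8% to 96.5% at n = 60. The choice should be made before the data are seen, since deciding on adjustment afterwards would weaken a one-sided test.

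### Is it a fault that the Hypothesis 2.2 correlations are tested one-sided, with the whole 5% family error in the predicted direction?

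*Combined protocol and SAP*

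**What the plan says.** The Statistical Analysis Plan words Specific Aim 2 without direction: "Determine if SWA disruption alters measures of mood, and measures of synaptic strength and plasticity in a sample of individuals with MDD". Its general method is also neutral: "Regression will be used to model if SWA is directly associated with mood, and synaptic strength/plasticity variables".

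Hypothesis 2.2 then gives a direction. Patients whose slow-wave activity (SWA) falls most are expected to improve most in synaptic strength and plasticity, which is a positive correlation. The test follows from this: "Since the scientific hypothesis is clearly one-sided, one-sided tests of the hypotheses of zero correlation will be performed", with Holm-Bonferroni over five comparisons. The plan adds: "the first test will be conducted at a 1-sided type 1 error rate of" 0.01.

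Hypothesis 1.2 concerns baseline values in patients with major depression (MDD). There, "lower values of synaptic strength and plasticity are predicted for subjects with lower SWA".

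**The concern.** A predicted direction is not by itself a reason for a one-sided test. The usual requirement is that an effect the other way is implausible or of no interest. The only reason visible in the text is "Since the scientific hypothesis is clearly one-sided", which restates the prediction.

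Three things make this look weak:

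- Aim 2 asks whether disruption changes the measures at all, without naming a direction.
- Hypothesis 1.2 links lower SWA to lower plasticity at baseline. If that relation also held within a person, lowering SWA would go with worsening, and the Hypothesis 2.2 correlation would be negative.
- The whole 5% lies in the favourable tail, twice what a two-sided 5% family would put there.

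At stake would be an easier positive claim, and a result in the unwelcome direction that counts formally as no association.

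**Working it through.** **Inputs.** From the Statistical Analysis Plan, Hypothesis 2.2: one-sided tests, five comparisons, Holm-Bonferroni, first step 0.01. The supplied text prints no family level, MDD sample size or expected correlation. The level is inferred below. Sample size n (20 to 60) and true correlation r (0.3 to 0.5) are assumptions.

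**1. The plan's own figure.** The first Holm step is the family level divided by the number of tests: 0.05/5 = 0.01, which matches. A one-sided family level of 0.025 would give 0.025/5 = 0.005, which does not. The implied family level is therefore 5 × 0.01 = 0.05, one-sided. The full sequence is 0.01, 0.0125, 0.0167, 0.025, 0.05.

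**2. Is the error controlled as stated?** For five independent true nulls, the chance of at least one rejection at the first step is 1 − 0.99^5 = 0.049, below 0.05. Holm keeps the family error at or below its level under any dependence. With 0.005 in that tail the chance would be 1 − 0.995^5 = 0.025. This is where the doubling comes from, but the 0.025 belongs to a different rule. Nothing in the documents commits Hypothesis 2.2 to it.

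**3. What a two-sided rule would cost.** With the Fisher-z approximation, power in the predicted direction is Φ(atanh(r)·√(n−3) − z), where z = 2.326 for 0.01 one-sided and 2.576 for 0.01 two-sided. For n = 40 and r = 0.4, atanh(0.4)·√37 = 2.577. Power is Φ(0.251) = 59.9% one-sided and Φ(0.001) = 50.0% two-sided.

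First-step power, one-sided to two-sided (%):

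| n | r = 0.3 | r = 0.4 | r = 0.5 |
|---|---|---|---|
| 20 | 14.7 to 9.7 | 28.1 to 20.4 | 47.5 to 37.8 |
| 30 | 23.6 to 16.7 | 45.0 to 35.4 | 70.1 to 61.0 |
| 40 | 32.9 to 24.4 | 59.9 to 50.0 | 84.5 to 77.8 |
| 60 | 50.4 to 40.6 | 80.8 to 73.3 | 96.6 to 94.2 |

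The loss is 2.4 to 9.9 percentage points. At the last step (0.05) the same formula gives a loss of 0.8 to 12.5 points.

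**4. What a two-sided rule would buy.** By symmetry, for a true r of −0.4 the two-sided first step would declare a negative correlation with power 20%, 35%, 50% and 73% at n = 20, 30, 40 and 60. The one-sided test never declares one. That follows from the definition of a one-sided test and does not show that the rule malfunctions.

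A natural example is borderline. An observed r = −0.40 at n = 40 gives p = 0.00997 by Fisher-z. The ordinary t-test gives |t| = 0.40·√38/√(1 − 0.16) = 2.69 on 38 degrees of freedom, so two-sided p = 0.0105. The exact critical value is 0.403, so this result would not pass the two-sided 0.01 step either.

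**5. Does the plan itself expect the opposite sign?** Hypothesis 1.2 is about differences between patients at baseline; Hypothesis 2.2 is about change within patients under disruption. The first does not determine the sign of the second. Where the plan speaks about disruption in MDD, it predicts benefit: Hypothesis 2.2 for plasticity and, in the same direction, Hypothesis 2.1, where lower SWA goes with lower negative mood scores. No passage predicts a negative correlation between the changes.

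**6. Would a negative correlation answer Aim 2?** Not by itself. Aim 2 asks whether disruption changes the measures. A correlation between individual changes can be negative while the average improves, stays level or worsens. Making the correlation test two-sided would not settle that question.

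**The case for a change.** The best case for two-sided tests is that disruption is an experimental manipulation in patients with depression. A finding that larger SWA reductions go with less improvement would matter, and the plan nowhere says that such a result is impossible or unimportant. The change would affect only wording, and the supplied text contains no power figure that it would break.

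Part of this stands. The visible justification is brief, an opposite sign is conceivable, and many statisticians would prefer two-sided tests here. The Aim 2 regression covers the same endpoints and is not labelled one-sided, but the supplied text gives it no error rate either, so it is no formal substitute.

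This does not make the choice an error. What is lost is a formal declaration within one family of five tests. The information remains, because a negative correlation would show in the estimate and in the regression. A two-sided confidence interval beside each correlation would show it more clearly at no cost in power, but that is an optional addition to reporting. Nor can one say that no fuller justification exists: the plan refers to methods described earlier, and that text is not among the pages supplied.

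**Conclusion.** The concern does not hold. The one-sided rule is prespecified, disclosed, consistent with the direction of Hypothesis 2.2 and correctly divided over five tests (0.05/5 = 0.01). Followed as written, it gives a sound conclusion on that hypothesis at an implied one-sided family error of 5%.

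The doubled error (0.01 against 0.005 at the first step) is a comparison with a rule the plan did not adopt. Two-sided testing would trade up to 9.9 percentage points of power at the first step, and up to 12.5 at the last, for the ability to declare a sign that the plan does not predict for change under disruption. Reasonable statisticians can differ on that trade.

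The power figures rest on assumed n of 20 to 60 and r of 0.3 to 0.5, and on the Fisher-z approximation. The 5% family level is inferred from the stated first step. The conclusion does not depend on the assumed n and r.

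### Does the optional comparison of MDD men and MDD women with all healthy controls undermine Hypothesis 3.1?

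*Combined protocol and SAP*

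**What the plan says.** All of this stands in the Statistical Analysis Plan, Specific Aim 3, unless noted.

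- **Default analysis.** The MDD sample is split into male and female groups of equal size. The plan then states: "The analyses described for Aims 1 and 2 will be repeated stratified by sex". For Aim 1 the repeated analysis is the MDD-versus-control comparison of baseline means, where (Specific Aim 1) "Hypotheses will be tested using two-sample t-tests with adjustment for multiple outcomes" is specified.
- **Between-sex contrast.** "statistical comparisons between sex will be performed and where appropriate 95% confidence intervals for differences between sex in relevant effect sizes will be constructed".
- **Added comparison and its reason.** The plan anticipates that any difference between the sexes will be larger in MDD than in controls. On that ground it adds a conditional step: "if sex differences in HC appear relatively small, the analyses for Aim 3 will also compare male MDD and female MDD to all HC".
- **Hypothesis 3.1.** MDD men are predicted to have lower values "compared to MDD females and HC at baseline".
- **Status.** The emphasis is descriptive, the plan states that it lacks power within sex, and "Results from Aim 3 will be considered hypothesis generating".

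The documents give no sample size, no sex split of the controls, no SD and no numerical meaning for a relatively small sex difference.

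**The concern.** Aim 3 asks whether men with MDD are more impaired than women with MDD. The obvious confounder is a sex difference that exists without depression. Comparing MDD men with same-sex controls removes it; comparing them with all controls does not. If healthy men score lower than healthy women on an outcome, the all-control comparison makes MDD men look more impaired than they are. If healthy men score higher, it hides part of a real deficit.

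Two features seem to make this worse. The comparison is run only after looking at the control data, under a condition with no threshold, test or rule for each outcome. And once it is run, Hypothesis 3.1 has two answers against controls, with nothing to say which counts if they disagree. At stake would be a claim of male-specific impairment that is really a normal sex difference.

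**Working it through.** The plan states no figure for Aim 3, so there is none to reproduce. The check has four steps.

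**1. What is planned by default.** The stratified repeat of Aim 1 comes first and carries no condition. The all-control comparison is joined to it by the word also. The sentence before names only the MDD sample as split by sex, but a sex-stratified MDD-versus-control comparison needs controls split the same way. A condition on the sex difference in controls would also have little purpose if all controls were already the default. The natural reading is same-sex comparison always, all-control comparison sometimes in addition.

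**2. Size of the shift.** Let d be the control male mean minus control female mean and f the female share of controls. The all-control mean equals the male control mean minus f × d, so

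- male MDD − all controls = (male MDD − male controls) + f × d
- female MDD − all controls = (female MDD − female controls) − (1 − f) × d

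This holds for the observed means as well as the true ones. With f = 0.5, the two male estimates differ by exactly half the observed control sex difference. If small means an observed difference under 0.2 or 0.3 SD, they differ by less than 0.10 or 0.15 SD. At an assumed 20 per sex per group and SD 1, the standard error against all controls is √(1/20 + 1/40) = 0.274 SD. The two answers will therefore usually be close.

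**3. False findings.** Assumptions: 20 per cell, controls half male, SD 1, no effect of diagnosis, the same true male-minus-female difference D in both groups, two-sided 0.05 counted in the lower tail (2.5%). Results are by simulation. The first two data rows count the all-control test alone; the last row counts either control test.

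| | men truly lower by 0.1 SD | 0.2 | 0.3 | 0.4 |
|---|---|---|---|---|
| All-control test shows MDD men lower | 3.7% | 5.4% | 7.5% | 10.1% |
| Condition met, observed difference under 0.3 SD | 63.0% | 56.3% | 46.8% | 35.6% |

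| Meaning of small | under 0.2 SD | under 0.3 SD | p > 0.05 |
|---|---|---|---|
| Condition met and all-control test false, D from −0.1 to −0.4 | 1.7% to 2.4% | 2.3% to 3.7% | 3.5% to 7.9% |

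Counting a false finding from either control test, with D from 0 to −0.4, the size-based conditions give about 3.1% to 4.7%; only the p > 0.05 reading reaches about 8%. The plan's wording concerns how large the difference looks, not whether it is significant. If men are truly higher by 0.2 or 0.4 SD, the all-control false rate falls to 1.0% or 0.3%.

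**4. What is gained.** With m per cell, the variance of the same-sex estimate is 2/m. The mean squared error of the all-control estimate is 1.5/m + D²/4.

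- m = 20, same-sex: 2/20 = 0.100
- m = 20, all controls, D = −0.2: 0.075 + 0.010 = 0.085
- m = 20, all controls, D = −0.4: 0.075 + 0.040 = 0.115
- Break-even: |D| = √(2/m) = 0.45, 0.32 and 0.26 SD at m = 10, 20 and 30

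Using the all-control estimate only when the condition is met (size-based, m = 20) gives 0.096 to 0.105. That is almost level with same-sex controls.

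**The case for a change.** The strongest counter-argument is that a difference that looks small need not be small. At 20 controls per sex, the 95% interval for the control sex difference has half-width 2.024 × √(2/20) = 0.64 SD, twice the 0.32 SD break-even. Under a loose reading of the condition the protection is weak. If the true difference is 0.5 SD and small means an observed difference under 0.5 SD, the condition is met in 49.6% of simulated trials. Among those, the all-control test falsely shows MDD men lower in 13.9%, against 4.4% for the same-sex test. Jointly that is 0.496 × 0.139 = 6.9%. An analyst could also apply the condition differently from one outcome to the next.

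That much stands: the threshold is missing and the two control comparisons are not ranked. It carries little weight here. The 0.5 SD case contradicts the plan's stated expectation about controls. The same-sex results are produced in every case, so any reader can see the gap, which is a fixed share of the observed control sex difference. The planned between-sex intervals for MDD-versus-control effects, taken from the stratified analysis, are the contrast of diagnosis by sex that guards against this confounding. That contrast is imprecise (half-width 1.992 × √(4/20) = 0.89 SD at 20 per cell), which is why a supplementary look with more controls has some appeal.

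One trap deserves notice. Subtracting the two all-control effects cancels the shared control mean and leaves only MDD men minus MDD women, with all of the normal sex difference in it. The plan does not propose that subtraction as a test of diagnosis by sex.

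**Conclusion.** The concern is correct as algebra but does not call for a change. The all-control comparison is supplementary, is run only when the control sex difference looks small, and has a stated reason. Under size-based readings it moves the male estimate by less than 0.10 to 0.15 SD, raises the chance of a false finding from 2.5% to about 3.1% to 4.7%, and leaves accuracy about level. No confirmatory error rate is attached to Hypothesis 3.1. Aim 2, Hypothesis 3.2 and the comparison of MDD men with MDD women are untouched.

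The undefined threshold and the unranked comparator are details that a competent analyst fills sensibly: read Hypothesis 3.1 against same-sex controls, and present the all-control result as secondary beside the control sex difference and its interval. Followed as written, the plan still reports the results needed for that.

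The figures rest on assumed cell sizes, an even sex split in controls, an assumed normal sex difference and assumed meanings of small. They illustrate scale and are not properties of this trial. With controls unbalanced by sex, the shifts become f × d for men and (1 − f) × d in the opposite direction for women. The precision cost of same-sex controls, about 15% here (0.316 against 0.274), would then differ by sex.
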